3.4.1 Missing Dates

The imputation of missing date components (i.e., missing day, month, or year values) for start/stop date of adverse events and prior/concomitant medications are described in the corresponding section where the date is discussed.

3.4.2 Missing Data for Efficacy Analyses

The methods for the handling of missing data for the efficacy analyses are described in the corresponding section where the analysis is discussed.

3.4.3 Calculations for the DEP Responder

As discussed in [Section 2.2](#), a responder is defined as a participant who achieves a $\geq 20\%$ reduction in blood Phe level compared to DEP baseline. The following are additional details regarding the definition of a responder:

- A participant will be considered a responder if they met the $\geq 20\%$ reduction in blood Phe level at any time in the DEP.
- This will include the scheduled Week 3 blood Phe assessments at the end of each 3-week dosing period.
- This will not include assessments that were made specific to the participants included in the DEP Weekly substudy ([Section 2.3.2](#)).

3.5 Analysis Populations

Analysis populations will be defined for each of the 3 parts of the study (DEP, RWP, and OLE).

Full analysis set (FAS): The full analysis sets are based on the intention-to-treat principle. The DEP FAS includes all participants enrolled in the DEP who take at least one dose of DEP study medication.

The RWP FAS is defined as all participants randomized into the RWP who take at least one dose of RWP study medication. Additionally:

- The responder RWP FAS is defined as participants in the RWP FAS who are responders
- The nonresponder RWP FAS is defined as participants in the RWP FAS who are nonresponders.

A responder is defined as a participant who achieves a $\geq 20\%$ reduction in blood Phe level compared to DEP baseline on SYNB1934v1.

The responder RWP FAS will be the primary efficacy analysis population for the RWP. Analyses on the RWP FAS will be performed according to the randomized treatment group.

In the event that, based on the interim analysis results utilizing the criteria provided in [Table 10](#), the DMC recommends dropping either the 1×10^{12} or the 1×10^{12} and 6×10^{11} doses the following will occur:

- The participants in the DEP who have an iTD corresponding to a dropped dose will go directly into the OLE part of the study (i.e., as opposed to being randomized into the RWP).
- The RWP FAS, responder RWP FAS, and nonresponder RWP FAS, will exclude all participants whose iTD dose level was dropped.

These participants who are excluded from the RWP FAS will be summarized separately.

Safety analysis set (SAS): For each of the 3 study parts, the SAS will include all participants who received any amount of IMP in the corresponding study part with treatment assignment based on the treatment received.

For the RWP the safety analyses will be presented for the RWP SAS overall as well as by responder/nonresponder subgroups. Similarly, the OLE safety analyses will be presented for the OLE SAS overall as well as by responder/nonresponder subgroups.

A participant will be considered receiving treatment if the eCRF question “did the patient receive any study drug doses” is answered “Yes” and there is a corresponding non-missing date.

Per-protocol analysis set (PPS): The DEP PPS is defined as all DEP FAS participants, who had no major protocol deviations that would affect efficacy, completed their final 3-week iTD, whose dietary Phe remained within 20% of their DEP baseline value (see [Section 3.10.2](#)), and who did not require systemic antibiotic treatment during DEP (see [Section 3.12](#)). The DEP PPS will be used as a sensitivity analysis for the DEP primary efficacy endpoint.

The responder RWP PPS is defined as all responder RWP FAS participants, who had no major protocol deviations that would affect efficacy, had at least 75% treatment compliance (see [Section 3.13.1](#)), whose dietary Phe remained within 20% of their DEP baseline value (see [Section 3.10.2](#)), and who did not require systemic antibiotic treatment during DEP or RWP (see [Section 3.12](#)).

The responder RWP PPS will be used as a sensitivity analysis for the RWP primary efficacy endpoint. RWP major protocol deviations will be determined in a blinded manner prior to the RWP database lock. Analyses on the responder RWP PPS will be performed according to the randomized treatment group.

Following the protocol deviations handling plan, major protocol deviations that would affect efficacy will be determined by a review of the functional team members (i.e., the set of functional team members will be defined in the protocol deviations handling plan), which will be blinded for the RWP.

RWP Randomized analysis set: The RWP Randomized analysis set is defined as all participants randomized into the RWP. The responder Randomized analysis set is defined as participants in the Randomized analysis set who are responders. The nonresponder Randomized analysis set is defined as participants in the Randomized analysis set who are nonresponders.

3.5.1 Subgroups

For selected efficacy and safety analyses (see [Section 3.14](#) and [Section 3.15](#), respectively) the summaries will be performed overall and by responder/nonresponder subgroups (i.e., as defined in [Section 3.5](#)).

The DEP will contain an optional substudy (DEP weekly substudy) to evaluate the range and variability of Phe and Tyr response at each dose level (see [Section 2.3.2](#)). The twenty participants in this substudy will have weekly Phe and Tyr value assessments during the DEP. The weekly Phe and Tyr assessments will be summarized for this subgroup.

The following additional subgroups will also be considered:

- Adolescents: Note that, for non-US sites, participants 12 to 17 years of age may be enrolled after the first 20 participants have completed the DEP, with approval of the DMC.
- Participants on sapropterin dihydrochloride (Kuvan) at the DEP baseline visit (i.e., DEP study day 1).
- Genotypic phenotype values (GPV) subgroups: For the subset of participants who have non-missing results for allele #1 and allele #2 (i.e., from the Genotyping eCRF page), their GPV will be calculated. The GPV will be calculated by entering the allele information into the following website <http://www.biopku.org/biopku/search-allele-start.asp>. The GPV is a number from 0 to 10; the following 3 subgroups will be considered based on the GPV score: 0-2.7, 2.8-6.6, 6.7-10.0.
- Participants in the DEP who had an iTD of a dose that was discontinued (i.e., this subgroup will only be utilized if a dose is discontinued as per the DMCs recommendation as defined in [Section 3.17](#)).
- Participants in the RWP who were excluded from the RWP FAS (i.e., this subgroup will only be utilized if a dose is discontinued as per the DMCs recommendation as defined in [Section 3.17](#)).

The analyses to be performed on these subgroups will be discussed in the corresponding efficacy and safety sections.

3.6 Participants Disposition and Evaluability

3.6.1 Participant Disposition

The following participant disposition is summarized using the analysis populations defined in [Section 3.5](#).

- The number of participants who entered the Screening Period (i.e., as defined by signing informed consent)
- The number and percent of participants rescreened (using the number screened as the denominator).

The following percentages will use the DEP FAS as the denominator:

- The number of participants enrolled in DEP (i.e., defined as being assigned study drug)
- The number and percent of participants completing/not completing the DEP (i.e., completed the DEP is defined as having completed the End of DEP/RWP Baseline Visit as indicated in the eCRF)
- The number and percent of participants who achieve an iTD
- The number and percent of responders.

The following percentages will use the RWP FAS as the denominator:

- The number of participants randomized into the RWP overall and by responder/nonresponder status
- The number and percent of participants completing/not completing the RWP (i.e., completed the RWP is defined as having a non-missing RWP Week 4 visit) overall and by responder/nonresponder.

The following percentages will use the OLE SAS as the denominator:

- The number of participants enrolled in OLE (i.e., defined as being assigned OLE study drug)
- The number and percent of participants completing the OLE/not completing the OLE (i.e., completing the study as determined by the eCRF question “Did the subject complete the study per protocol?”).

Note: The number and percent of participants who did not complete each of the 3 study parts will be summarized along with the reason:

- LOST TO FOLLOW-UP
- PROTOCOL DEVIATION
- ADVERSE EVENT
- LOW LEVELS OF PHE OR TYR OR PROFOUND ELEVATION IN PHE
- PREGNANCY
- STUDY TERMINATED BY SPONSOR
- PHYSICIAN DECISION
- WITHDRAWAL BY SUBJECT
- NON-COMPLIANCE WITH STUDY DRUG
- DEATH
- OTHER.

The summaries will be overall for Part 1; overall, responder status, and treatment group (i.e., active or placebo) for Part 2; and overall and responder status for Part 3.

3.6.2 Protocol Deviations

The protocol deviations will be shown in a participant listing, by study part and treatment group (for the RWP).

For the RWP, the determination of major protocol deviations and major protocol deviations that would impact efficacy (i.e., a criterion for the RWP PPS as defined in [Section 3.5](#)) will be performed in a blinded manner.

3.7 Demographics

Demographics will be summarized for the following analysis Populations:

- DEP: FAS and SAS
- RWP: FAS, SAS, PPS
- OLE: SAS.

For each analysis population the summary will be overall and by treatment group for the RWP (i.e., SYNB1934v1 and Placebo). For the RWP, results will also be presented by responder/nonresponder.

Descriptive statistics for continuous variables will be provided for age (at time of informed consent), height, weight, and BMI. Frequency counts and percentages will be tabulated for sex, fertility status (for females), race, and ethnicity.

3.8 Baseline Characteristics

Baseline characteristics will be summarized for the DEP FAS, DEP SAS, RWP FAS, RWP SAS, and responder RWP FAS analysis populations.

The following information will be summarized for the DEP populations:

- Screening Phe
- DEP Baseline Phe
- DEP Baseline Phe intake
- DEP Baseline tyrosine (Tyr)
- Sapropterin dihydrochloride (Kuvan) at DEP Baseline (Yes/No)
- Current Proton pump inhibitor (PPI) Use at DEP Screening (Yes/No).

The following information will be summarized for the RWP populations:

- Screening Phe
- DEP Baseline Phe
- DEP Baseline Phe intake
- RWP Baseline Phe
- DEP Baseline tyrosine (Tyr)
- RWP Baseline tyrosine (Tyr)
- Sapropterin dihydrochloride (Kuvan) at DEP Baseline (Yes/No)

- Current Proton pump inhibitor (PPI) Use at DEP Screening (Yes/No).

3.9 Medical History

Medical history will be summarized for the DEP SAS. Medical history will be coded using MedDRA version 25.1 (or higher). The coded Preferred Terms (PT) will be summarized overall for the DEP SAS and, for the RWP SAS, by responder/nonresponder within each treatment group, and overall. A participant will be counted only once for each preferred term. The summary will present the results alphabetically by System Organ Class (SOC) and, within SOC, by decreasing frequency for the PT.

3.10 Prior and Concomitant Medications/Procedures

Prior and concomitant medications will be coded using WHO Drug (Version: B3 Global September 2022)

The incidence of prior medication will be presented by therapeutic class, and preferred (generic) drug name for the DEP SAS.

For the DEP and OLE study periods, the incidence of concomitant medication will be presented by therapeutic class, and preferred (generic) drug name for the corresponding SAS. A participant is counted only once for each therapeutic class and for each preferred drug name.

A participant is counted only once for each therapeutic class and for each preferred drug name.

Prior medications are defined as those taken and stopped prior to the date of first study treatment in the DEP. Any medication given at least once on or after the DEP first study treatment date will be defined as a concomitant medication including those which were started before first study treatment date and continued after first study treatment date.

Where a medication start date is partially or fully missing, and it is unclear as to whether the medication is prior or concomitant, it will be assumed that it is a concomitant medication.

Note that PPI and H2 blocker use will be summarized separately (see [Section 3.10.1](#))

3.10.1 PPI and H2 Blocker Use

PPI and H2 blocker use is captured on a specific eCRF page. PPI and H2 use will be summarized (separately) using the same methodology described in [Section 3.10](#) (separate listings as well).

3.10.2 [REDACTED] Use

[REDACTED] use is captured on a specific eCRF page. [REDACTED] use will be summarized (separately) using the same methodology described in [Section 3.10](#) (separate listings as well).

3.11 Dietary Phe

For 3 consecutive days prior to all scheduled study visits and blood Phe draws (see Schedule of Events [Table 11](#) and [Table 12](#)), all participants will have a 3-day dietary intake assessment. Participants will follow their usual diet (including Phe, protein, and medical food intake) from baseline in the DEP to the end of the RWP.

The following information will be summarized for the 3-day DEP Baseline Period:

- Calories (KCAL)
- Total Protein (grams)
- Natural Protein (grams)
- Medical Food Protein (grams)
- Phe (grams).

The following information will be summarized for the DEP, RWP, and OLE Periods using the corresponding SAS:

- At each scheduled visit, the percent change from baseline in 3-day dietary Phe levels will be summarized
- For the DEP and RWP, the number and of times a participant's 3-day Phe exceeded the within \pm 20% (inclusive) DEP baseline Phe criterion.

Note: the 3-day dietary endpoints to be summarized are the 3-day averages which are provided on the corresponding eCRF page.

For the DEP and OLE, the results will be presented overall. For the RWP, the results will be summarized by treatment group and responder/nonresponder within each treatment group.

3.12 Systemic Antibiotic Treatment

Systemic antibiotic treatment is defined as any concomitant medication antibiotic in which the route is oral, intravenous, or intramuscular. Any topical use is specifically not systemic. This 'topical use' includes antibiotics applied to any reachable area (most often the eye and ear canal).

The number and percent of participants using systemic antibiotic treatment will be summarized for the DEP, RWP, and OLE Periods using the corresponding SAS. For the DEP and OLE, and the results will be presented overall. For the RWP, the results will be summarized by treatment group and responder/nonresponder within each treatment group.

3.13 Treatment Compliance and Exposure

3.13.1 Compliance to Study Treatment

Compliance rates will be calculated for each of the 3 study periods (DEP, RWP, and OLE) using the following methodology:

For a participant, the compliance at each of the 3 individual dose levels received (3×10^{11} , 6×10^{11} , 1×10^{12}), will be calculated by the following:

$$\% \text{ Compliance} = 100 \times \frac{\# \text{ of sachets given} - (\# \text{ of sachets returned} + \# \text{ of sachets lost or destroyed})}{\text{Expected } \# \text{ of sachets to be taken}}$$

Here:

of sachets given: is determined by the number of kits given for the corresponding dose level

For each dose level kit there are 30 additional sachets provided in case of delayed visits, destroyed sachets, etc. In addition, for dose levels 6×10^{11} and 1×10^{12} there are 30 additional sachets in each kit for the lower dose levels of 3×10^{11} and 6×10^{11} , respectively, in case a dose reduction is needed. If a participant requires a dose reduction, they will use the additional sachets from the existing kit until a new kit is received. Study drug administration and study drug accountability will be completed at the dose level in EDC.

of sachets returned: is determined by the “Number of [individual dose level] sachets returned” field on the drug accountability CRF page for the corresponding dose level

of sachets lost or destroyed: is determined by the “Number of sachets lost or destroyed” field on the drug accountability CRF page for the corresponding dose level

Expected # of sachets to be taken: is determined by taking the difference between the “Start date” and “Stop date” on the study drug administration CRF for the corresponding dose level and accounting for either the dose ramp schedule for the DEP and OLE or three sachets a day for the RWP.

For the DEP and OLE and the expected number of sachets follows the following dose ramp schedule. Dose frequency is linked to an individual sachet (e.g., TID is 3 sachets). De-escalation of dose is possible at any point during the dose ramp. When a participant has de-escalated the expected # of sachets to be taken will be calculated by the actual number of days spent at the dose level.

Table 8: DEP and OLE Dose Ramp Schedule

	Dose Level 1			Dose Level 2			Dose Level 3		
Timing	D1-9	D10-14	D15-21	Wk 4	Wk 5	Wk 6	Wk 7	Wk 8	Wk 9
Dose (live cells)	██████████ $3 \times 10^{11}*$	3×10^{11}	3×10^{11}	6×10^{11}	6×10^{11}	6×10^{11}	1×10^{12}	1×10^{12}	1×10^{12}
Frequency	QD, D1-3	QD, D10-11	TID	QD \times 3 days	TID	TID	QD \times 3 days	TID	TID
	BID, D4-6	BID, D12-14		BID \times 4 days			BID \times 4 days		
	TID, D7-9								

BID = twice per day; D = day; QD = once per day; TID = 3 times per day.

* See Section 4.3.1 of the study protocol for details.

For the RWP Period, the compliance rate will be the compliance rate for the corresponding dose level the participant was on during the RWP (i.e., dose modification is not allowed during the RWP).

For each of the 3 study periods (DEP, RWP, and OLE), compliance will be summarized using the SAS (defined in [Section 3.5](#)), with results also being presented by:

- For the DEP: By dose level
- For the RWP: By treatment group, responder/nonresponder subgroups, and treatment group within responder/nonresponder subgroups
- For the OLE: By dose level, responder/nonresponder subgroups

In addition to summary statistics for the compliance rate, the number and percentage of participants whose compliance rate is $\geq 75\%$ will be reported.

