#### **4.3.3. Treatment Compliance**

Study participants will prepare the individual doses at home. They will be instructed on the required procedures by trained study personnel and will receive written instructions on IMP preparation and storage. Compliance will be assessed by recording the number of sachets received and used by each participant. Participants who take  $\geq 75\%$  of doses will be considered compliant.

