2.2 STUDY DESIGN

This is a 3-part, Phase 3 study consisting of a dose-escalating, open-label period (DEP; Part 1) of up to 15 weeks, followed by a 4-week, double-blind, placebo-controlled, randomized withdrawal period (RWP; Part 2), and an open-label extension (OLE; Part 3) of up to 36 months. [Figure 1](#) presents a study schematic.

In the DEP, all enrolled participants will maintain a stable diet reflecting their baseline Phe intake and receive escalating doses of SYNB1934v1 from approximately 3 to 15 weeks to determine an iTD, which is defined as the highest dose the participant is able to tolerate. A participant will be defined as having reached an iTD if they tolerate 3 weeks at a dose, regardless of whether other doses are tolerated.

Blood Phe level will be measured at each dose level after 3 weeks at that level. A responder will be defined as a participant who achieves a $\geq 20\%$ reduction in blood Phe level compared to DEP baseline on their iTD. For inclusion in the RWP primary efficacy analysis population, response will be assessed at the third week of a participant's established iTD for SYNB1934v1.

If at any time during a 3-week dosing interval in the DEP the participant or investigator considers a dose level to be intolerable, the dose may be de-escalated after discussion with the medical monitor. In this case, the participant will restart 3 weeks at the lower level iTD. After de-escalation, participants cannot escalate to a higher dose again during.

[figure not shown]
The DEP will contain an optional substudy (DEP weekly substudy) to evaluate the range and variability of [REDACTED] at each dose level. The [REDACTED] participants in this substudy will have weekly Phe and Tyr value assessments during the DEP (i.e., with Tyr assessments being primarily assessed for safety).

Once the first [REDACTED] participants have attained an iTD and completed the DEP or the [REDACTED] has a baseline DEP and has been in the study for [REDACTED], whichever occurs earlier, the DEP data will be evaluated by an independent Data Monitoring Committee (DMC). The DMC will use a pre-specified set of criteria based on both safety and efficacy to determine whether the dose regimen is appropriate or whether any doses should be discontinued as well as whether the study should be stopped for futility. Enrollment will not be paused during the interim analysis.

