3.13.2 Treatment Duration

For each of the 3 study periods treatment duration will be Last dose date – First dose date + 1.

For each of the 3 study periods (DEP, RWP, and OLE), treatment duration will be summarized using the SAS populations (defined in [Section 3.5](#)), with results also being presented by responder/nonresponder and treatment group within responder/nonresponder subgroups for the RWP and OLE.

Additionally for the DEP, the duration of time (i.e., days) that a participant was on a dose level that the participant discontinued from will be summarized by dose level and overall.

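### RWP compliance is measured only up to the participant's own stop date, so someone who stops study drug early can pass the 75% rule and stay in the responder RWP PPS

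*SAP*

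**What the plan says.** SAP 3.13.1 defines compliance as sachets given, minus those returned and those lost or destroyed, divided by the sachets expected, times 100. The expected number "is determined by taking the difference between the" start and stop dates recorded for the dose level, with "three sachets a day for the RWP". The planned length of the period does not enter. SAP 2.2 gives that length: the DEP is "followed by a 4-week, double-blind, placebo-controlled, randomized withdrawal period (RWP; Part 2").

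The next section counts days differently. Under SAP 3.13.2, "treatment duration will be Last dose date – First dose date + 1".

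The responder RWP PPS in SAP 3.5 is limited to participants who "had at least 75% treatment compliance", with a cross-reference to 3.13.1. They must also have no major deviation affecting efficacy, dietary Phe within 20% of DEP baseline, and no systemic antibiotics. The DEP PPS, defined just above it, additionally requires the last three weeks at the iTD to have been completed. The RWP set has no counterpart to this.

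Protocol 4.3.3 sets the threshold at 75% and says participants who take that share "of doses will be considered compliant". It does not say whether this means scheduled doses or doses due before stopping. Protocol 3.5 encourages those who stop study drug in the RWP to stay and complete their assessments, and Protocol 5.6 has them attend the RWP visits as scheduled.

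**The concern.** A per-protocol set is meant to show the treatment effect among people who took the treatment broadly as planned. When the denominator ends at the participant's own stop date, permanent discontinuation never counts against compliance. Only doses missed before that date do. No other written criterion for the responder RWP PPS automatically removes an early stopper, and the follow-up rules make it likely that such a person has a Week 4 Phe value.

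SAP 3.14.2.3 re-runs the primary analysis on this set, so the Week 4 value would be used. Protocol 1.6 states that Phe reaches steady state within 5 days. An active-arm participant who stops on Day 7 would therefore be expected to be fully off-drug by Day 28. Keeping such people pulls the two arms together in the analysis that is supposed to reflect adherence.

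**Working it through.** The documents report no worked compliance figure, so there is none to reproduce. The check applies the SAP formula to simple cases.

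**Inputs.** Three sachets a day in the RWP and the date-difference rule (SAP 3.13.1); a four-week RWP, so 28 days (SAP 2.2); the 75% threshold (SAP 3.5, Protocol 4.3.3); the inclusive day count (SAP 3.13.2). Assumption: the stop date is the actual last dosing day. The SAP does not define it.

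**Step 1: early stopping with every dose taken up to the last dosing day d.** Sachets taken = 3d. Three denominators are compared:
- as written: 3 × (d − 1)
- inclusive: 3 × d
- planned: 3 × 28 = 84

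| Last dosing day | Taken | As written | Inclusive | Planned |
|---|---|---|---|---|
| 2 | 6 | 6/3 = 200% | 100% | 6/84 = 7.1% |
| 7 | 21 | 21/18 = 116.7% | 100% | 21/84 = 25.0% |
| 14 | 42 | 42/39 = 107.7% | 100% | 42/84 = 50.0% |
| 20 | 60 | 60/57 = 105.3% | 100% | 60/84 = 71.4% |
| 21 | 63 | 63/60 = 105.0% | 100% | 63/84 = 75.0% |
| 28 | 84 | 84/81 = 103.7% | 100% | 100% |

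Every row passes 75% under both date-based denominators. Against the planned doses, full-adherence stoppers before Day 21 fail. Adding the missing day removes the scores above 100% but does not change who passes in this table.

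**Step 2: the missing day over a full course.** Expected sachets: 3 × 27 = 81 as written, against 3 × 28 = 84. Pass mark: 0.75 × 84 = 63, against 0.75 × 81 = 60.75, which means 61 sachets. Someone who takes 61 scores 61/81 = 75.3% as written but 61/84 = 72.6% of the schedule. Over a full course, only participants who take exactly 61 or 62 sachets change status. The distortion is larger for short courses. A one-day course has a denominator of zero.

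**Step 3: possible effect on the PPS estimate.** The documents do not say how many participants will stop study drug and stay on study. Suppose a fraction f of the active arm does so and reverts fully to placebo levels, while placebo stoppers are unaffected. The planned difference of −245 µmol/L (Protocol synopsis, sample size) then shrinks by f × 245, which is 2.45 µmol/L per percentage point. Taking the 5% RWP drop-out assumption as a stand-in for f gives 0.05 × 245 = 12.25 µmol/L. This is an illustration, since drop-out and stopping drug while staying on study are different events.

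**The case against.** The strongest reply is that adherence while on treatment is a legitimate measure, provided discontinuation is reported separately. The SAP does report it: treatment duration in 3.13.2, and RWP non-completion with reasons in 3.6.1. SAP 3.14.2.3 also plans an analysis of the RWP primary endpoint that drops observations after treatment discontinuation, which removes the off-drug values at issue here. This stands, and it limits the harm. It does not correct PPS membership: the rule still labels as compliant someone who took a quarter of the planned doses.

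On the day count, the literal reading may not be the intended one. Table 8 counts ramp days inclusively, and the de-escalation rule in 3.13.1 speaks of actual days at the dose level. The 117% and 200% figures depend on the literal reading and become 100% without it. That is fair, and the main point survives at 100%.

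Three stronger readings are tempting but unsupported.

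- **Early stoppers necessarily remain in the PPS.** A blinded review of major deviations, under a separate plan not provided here, could exclude some of them. They can remain; it is not shown that they will.
- **The spare sachets also help early stoppers pass.** Sachets given "is determined by the number of kits given for the corresponding dose level", and returned and lost sachets are subtracted. If the 30 same-level spares are counted as given and returned, the result is (114 − 30)/84 = 100%. If they were left out of the given count but included in the returned count, a fully adherent participant would score (84 − 30)/84 = 64.3%, which is the opposite direction. Only spares neither returned nor recorded as lost would raise the score. The lower-dose spares are for dose reduction, which is barred in the RWP, and the DEP PPS has no compliance rule. How these spares enter the count is at most a wording question for DEP and OLE accountability, and it depends on form conventions that the documents do not show.
- **The primary result is at risk.** The primary analysis uses the responder RWP FAS with a treatment-policy strategy and does not use the compliance rule. Retained active-arm stoppers would be expected to dilute the PPS difference; they would not create a false positive.

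**Conclusion.** The point holds for the stop-date denominator combined with the lack of a completion criterion in the responder RWP PPS. Under the rule as written, a participant with full adherence up to an early permanent stop scores at least 100% on any stop day from Day 2 onward, while having taken as little as 7.1% of the planned doses (25% for a Day 7 stop). The missing day is a real inconsistency with SAP 3.13.2 but is secondary: two sachets on the pass mark over a full course.

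The conclusion assumes that the recorded stop date is the last dosing day and that the deviation review does not remove the participant. The impact is modest: the PPS is a sensitivity set, the assumed RWP drop-out is 5%, and a separate analysis already excludes post-discontinuation observations. It is still worth correcting, because the PPS does not do what its 75% rule suggests and the correction is a matter of wording.

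**What to change.** In SAP 3.5 and 3.13.1, for responder RWP PPS membership, divide sachets taken by the planned 28 × 3 = 84 for anyone who discontinues study drug early. Alternatively, add a completion criterion to the responder RWP PPS, parallel to the one in the DEP PPS. The two differ slightly: with the planned denominator, a fully adherent participant who stops on or after Day 21 still passes, whereas a completion criterion would remove that person. The SAP should say which is meant.

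Wherever actual dates are kept, use stop − start + 1, in line with SAP 3.13.2. This suits RWP completers, whose visits may fall within a 3-day window, so that their period need not be exactly 28 days. Define the stop date as the last dosing day.

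The cost is a few lines of SAP text, agreed before unblinding, and slightly fewer participants in the PPS.
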